6.10 Criteria and Procedures for Study Termination

A patient's follow-up in the study will end after:

- 1) Failure to deploy the device + 30 days;
- 2) Conversion to open surgical repair + 30 days;
- 3) Patient withdrawal or lost to follow-up;
- 4) Patient death;
- 5) Closure of the investigation; or
- 6) Completion of all scheduled clinical and imaging visits through 5 years.

An autopsy, including explant of the study device, may be requested for patients who die with a study device in place. Both the excised aorta and the study device should be sent to the Data Coordinating Center for subsequent examination. Any study device excised in the course of conversion to open repair should also be sent to the Data Coordinating Center. Further instructions will be provided as needed. Data will be collected and stored in a database.

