7.0 Statistical Considerations

7.1 Sample Size Calculations

The 30-day mortality rate is estimated to be 7.6%^{2,6,9-14} based on a literature review of patients treated with endovascular repair for BTAI. The data used to calculate the mortality rate are provided in Appendix E. Forty-three patients are required to construct a 95% confidence interval with a margin of error of 8%. A total of 50 patients will be enrolled to account for possible loss to follow-up or withdrawal from the study. Up to 30 centers in the US and outside the US may participate.

The following formula is used to calculate the sample size: $n = \frac{z_{0.975}^2 p(1-p)}{\Delta^2}$, where $z_{0.975}$ is the 97.5th quantile, p is the performance goal, and Δ is the margin of error (8%). With 43 patients, a 95% confidence interval for the 30-day mortality rate would be [0%, 15.6%].

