7.4 Missing Data

Missing data will be addressed using three primary strategies: 1) estimating missing data with the best available data, 2) case deletion, and 3) multiple imputation.

The first strategy may be used for missing imaging data. Previous clinical trial experience suggests that some portion of the imaging data may not meet the criteria for accurate measurements by the core laboratory. However, it is recognized that the investigator uses

this information to provide the best possible care for the patient. Therefore, it is reasonable to substitute any missing core laboratory measurements with the corresponding measurements made by the investigator (or his/her staff). In addition, the absence or presence of clinical sequelae may provide the required missing core laboratory assessment of device performance. Furthermore, imaging at subsequent time points may be available, making it possible to infer patient status at the time point of interest. This strategy is a best approximation of the missing data value.

The second strategy is case deletion. If the amount of missing data does not result in a reduction of analyzable patients to a number that is below that required for sufficient statistical power of the primary endpoints, then case deletion will be the method of choice for that analysis.

The third strategy is multiple imputation. This method will be used to predict missing endpoint data. For missing primary endpoint data, the multiple imputation technique will be used to generate random Bernoulli observations with probabilities equivalent to the proportion of (non-missing) “Yes”/ “No” entries. It is anticipated that no covariates will be used for this model. This model-based imputation exercise may provide estimates of the missing data that can be utilized in estimating event rates and confidence bounds. Strategies originating from Schafer¹⁵ will be used, supplemented with notes provided by Schafer.¹⁶ The computations will be performed using PROC MI and PROC MIANALYZE in SAS version 9.1 or later. Unless evidence suggests otherwise, missing at random data will be assumed.

Additional analyses of missing data may be performed as appropriate, including a tipping point analysis.

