10.5 Criteria and Procedures for Withdrawal

Subjects may withdraw from the study at any time without penalty or loss of benefits. The investigator may also decide to withdraw a subject from the study at any time on the basis of medical judgment. The investigator must make a reasonable effort to ascertain and record the reason for withdrawal or discontinuation for each patient while fully respecting the patient's rights. The reasons for withdrawal and discontinuation of any patient from the investigation shall be recorded. If such discontinuation is because of problems with safety or lack of effectiveness, that patient shall still be followed up in the investigation, if possible.

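### Sections 6.10 and 10.5 give different rules on follow-up after withdrawal, so outcomes after withdrawal may go uncollected

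*Combined protocol and SAP*

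**What the plan says.** Section 6.10 opens its list with "A patient's follow-up in the study will end after". Item 3 is "Patient withdrawal or lost to follow-up". It makes no distinction by reason or by who decides, and does not mention Section 10.5. Items 1 and 2 (failed deployment, conversion to open repair) each carry a further 30 days of follow-up; item 3 carries none.

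Section 10.5 covers withdrawal by the subject and by the investigator: "The investigator may also decide to withdraw a subject from the study at any time on the basis of medical judgment". It then adds: "If such discontinuation is because of problems with safety or lack of effectiveness, that patient shall still be followed up in the investigation, if possible".

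Section 7.4 has three strategies for missing data: substitution of the best available data (mainly for imaging), case deletion and multiple imputation. If enough analysable patients remain, "then case deletion will be the method of choice for that analysis". Imputation of a primary endpoint draws from the observed proportion and is expected to use no covariates. Missing at random is the default assumption, and a tipping point analysis is optional.

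**The concern.** The device is implanted once, so withdrawing a patient afterwards mainly stops data collection. Up to 30 centres could apply the two sections differently. A centre that follows 6.10 stops observing a patient whom 10.5 wants observed.

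Patients discontinued for safety or lack of effectiveness may plausibly differ in later risk from those who stay. If so, their missing outcomes are informative, and the default in 7.4 treats them as if they were not. The study is single-arm and descriptive, so the observed rates are its result. Section 7.5 also foresees using them as prior information for later device variations.

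**Working it through.** **1. The two rules side by side**

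| Situation | Section 6.10(3) | Section 10.5 |
|---|---|---|
| Patient withdraws, reason unrelated to safety or effectiveness | Follow-up ends | No rule on further follow-up |
| Patient withdraws over safety or lack of effectiveness | Follow-up ends | Arguably still followed, if possible |
| Investigator withdraws patient for safety or lack of effectiveness | Ends, if withdrawal includes the investigator's decision; otherwise not addressed | Still followed, if possible |
| Investigator withdraws patient for another medical reason | As in the row above | No rule on further follow-up |

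The second and third rows conflict or are unclear. Neither section says which governs.

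**2. Which outcomes are exposed**

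- Before withdrawal: recorded and kept. A collapse, a reintervention for type I or III endoleak, or a conversion that has already occurred is a known device-success failure.
- From withdrawal to day 30: deaths and device-success events are unobserved if 6.10 is applied. Only withdrawals before day 30 matter here.
- After day 30: all secondary endpoints through 5 years (Section 5.2) are unobserved. This is the longer and larger exposure.

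**3. The plan's own numbers**

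Section 7.1 uses n = z²p(1−p)/Δ² with p = 0.076 and Δ = 0.08. With z = 1.96, n = 3.8415 × 0.076 × 0.924 / 0.0064 = 42.15, rounded up to 43. This reproduces the plan's figure. Enrolling 50 leaves 50 − 43 = 7 patients (14%) for loss or withdrawal. Section 7.4 ties case deletion to a number needed for power, but the plan has no power calculation. I take 43 as the intended threshold, so up to seven patients could be deleted before imputation is called for.

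**4. Effect of deletion**

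With D true events in 50, and m patients lost of whom e have the event, the observed rate is (D − e)/(50 − m). It equals D/50 only when e/m = D/50. The documents give no withdrawal rate by reason, so D, m and e are assumptions. Take D = 4 (8.0%, exact 95% CI 2.2% to 19.2%):

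| Lost (m) | Deaths among lost (e) | Observed | Exact 95% CI |
|---|---|---|---|
| 1 | 1 | 3/49 = 6.1% | 1.3% to 16.9% |
| 2 | 2 | 2/48 = 4.2% | 0.5% to 14.3% |
| 7 | 0 | 4/43 = 9.3% | 2.6% to 22.1% |
| 7 | 1 | 3/43 = 7.0% | 1.5% to 19.1% |
| 7 | 2 | 2/43 = 4.7% | 0.6% to 15.8% |
| 7 | 3 | 1/43 = 2.3% | 0.1% to 12.3% |

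These are scenarios, not bounds: if all four deaths were among the lost, the observed rate would be 0. With m = 7, the rate is unbiased at e = 7 × 0.08 = 0.56 deaths. None among the lost overstates mortality; one or more understates it.

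**5. Effect of imputation**

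Let r = (D − e)/(50 − m). Imputing the m missing values at rate r gives an expected rate of [(D − e) + m·r]/50 = [(50 − m)·r + m·r]/50 = r. This is the same as case deletion, so the fallback does not remove the bias either.

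**The case against.** The strongest reply is that the sections can be read together. In 6.10 the wording can mean the patient's own decision, while 10.5 is the dedicated section and sets the specific rule. On that reading there is an ambiguity rather than a flat contradiction. This is a fair reading, but the documents do not draw the line. Section 10.5 uses the same verb for subject and investigator, and its follow-up rule is not limited to investigator decisions. If 6.10(3) does exclude investigator withdrawals, then 6.10 does not address them at all.

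Several further points stand:

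- The rule in 10.5 applies only where possible, so it is not an unconditional requirement.
- Failed deployment and conversion already have 30 more days under 6.10, and failures recorded before withdrawal are not missing.
- Best-available-data substitution may recover some imaging outcomes. It cannot supply vital status or later imaging that was never collected.
- The endpoints are descriptive, and no pass/fail decision turns on this.

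A reader might infer that both primary endpoints are biased in the device's favour. The documents do not support that. No withdrawal rates are given, few withdrawals may fall before day 30, and the table shows the mortality rate moving either way. For device success the effect can also be unfavourable: a patient who withdraws after a recorded failure still counts, while one who withdraws without a failure may be deleted.

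**Conclusion.** The point holds as an inconsistency that should be repaired, not as a demonstrated bias. Sections 6.10(3) and 10.5 give different instructions for patients discontinued over safety or lack of effectiveness, with no cross-reference. If sites apply 6.10, outcomes after withdrawal are lost: some before day 30, and mainly the 5-year secondary endpoints. Neither case deletion nor observed-rate imputation corrects the loss if those patients have excess events.

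That they do have excess events is a reasonable inference, not a documented fact. Each patient is worth 2 percentage points (1/50). The illustrative 2.3% to 9.3%, against a true 8.0%, rests on an assumed four deaths and seven losses with three to none of those deaths among them. It shows sensitivity only; the actual size and direction cannot be computed from the documents.

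**What to change.** - **Section 6.10(3):** limit it to withdrawal of consent for further follow-up, or loss to follow-up, and cross-refer to 10.5.
- **Section 10.5:** add a provision that patients withdrawn by the investigator who have not withdrawn consent stay in data collection for at least vital status and the 30-day endpoint assessments and, where possible, the later visits. This is new and extends 10.5: the present text names neither assessment and covers only discontinuation for safety or lack of effectiveness.
- **At withdrawal of consent:** ask permission to keep collecting vital status.

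The cost is about one sentence in each section and a few extra patient contacts. The changes concern data collection only, and the required 43 and enrolled 50 are unaffected.

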7.0 Statistical Considerations

7.1 Sample Size Calculations

The 30-day mortality rate is estimated to be 7.6%^{2,6,9-14} based on a literature review of patients treated with endovascular repair for BTAI. The data used to calculate the mortality rate are provided in Appendix E. Forty-three patients are required to construct a 95% confidence interval with a margin of error of 8%. A total of 50 patients will be enrolled to account for possible loss to follow-up or withdrawal from the study. Up to 30 centers in the US and outside the US may participate.

The following formula is used to calculate the sample size: $n = \frac{z_{0.975}^2 p(1-p)}{\Delta^2}$, where $z_{0.975}$ is the 97.5th quantile, p is the performance goal, and Δ is the margin of error (8%). With 43 patients, a 95% confidence interval for the 30-day mortality rate would be [0%, 15.6%].

7.2 Performance Goals

The primary and secondary endpoints of this study will be analyzed using only descriptive statistics, and will not be analyzed for the purpose of statistical inference, as these patients

typically have extensive concomitant injuries that would confound the interpretation of statistical comparisons to alternative treatments.

7.3 Site-level Poolability

Poolability of data from multiple sites will be verified by examining the primary and secondary safety and effectiveness measures among sites as well as important patient baseline characteristics. Site-level poolability will be considered appropriate provided that these measures are similar among sites.

It is expected that many sites will have too few patients to provide reasonable site-level estimates of primary, secondary, and baseline measures. Each investigative site will be allowed to enroll no more than 10 patients (20% of the total enrollment) to ensure the overall result is not biased by the results from a single site. Pooling of this information will be explored based on hospital size (large versus small), site enrollment (large versus small), type of hospital (community versus teaching), and other group-wise strategies.

It is recognized that patient baseline characteristics may differ among sites, with some sites routinely treating patients with more severe aortic injuries. It is anticipated that the primary and secondary endpoint measures may be related to covariates that reflect this severity, which are in turn related to outcome. Thus, any observed site-specific differences among the primary or secondary endpoints will be checked for confounding with other measured covariates. This can be accomplished using regression models (linear and logistic where appropriate) that include site and other measured covariates as independent variables.

Should one or more sites significantly differ from the rest, then all subsequent analyses will include the discriminating covariate or a covariate to distinguish between the unusual site(s) and those sites that are considered poolable.

7.4 Missing Data

Missing data will be addressed using three primary strategies: 1) estimating missing data with the best available data, 2) case deletion, and 3) multiple imputation.

The first strategy may be used for missing imaging data. Previous clinical trial experience suggests that some portion of the imaging data may not meet the criteria for accurate measurements by the core laboratory. However, it is recognized that the investigator uses

this information to provide the best possible care for the patient. Therefore, it is reasonable to substitute any missing core laboratory measurements with the corresponding measurements made by the investigator (or his/her staff). In addition, the absence or presence of clinical sequelae may provide the required missing core laboratory assessment of device performance. Furthermore, imaging at subsequent time points may be available, making it possible to infer patient status at the time point of interest. This strategy is a best approximation of the missing data value.

The second strategy is case deletion. If the amount of missing data does not result in a reduction of analyzable patients to a number that is below that required for sufficient statistical power of the primary endpoints, then case deletion will be the method of choice for that analysis.

The third strategy is multiple imputation. This method will be used to predict missing endpoint data. For missing primary endpoint data, the multiple imputation technique will be used to generate random Bernoulli observations with probabilities equivalent to the proportion of (non-missing) “Yes”/ “No” entries. It is anticipated that no covariates will be used for this model. This model-based imputation exercise may provide estimates of the missing data that can be utilized in estimating event rates and confidence bounds. Strategies originating from Schafer¹⁵ will be used, supplemented with notes provided by Schafer.¹⁶ The computations will be performed using PROC MI and PROC MIANALYZE in SAS version 9.1 or later. Unless evidence suggests otherwise, missing at random data will be assumed.

Additional analyses of missing data may be performed as appropriate, including a tipping point analysis.

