3.2 Secondary Objectives

Additional objectives for descriptive purposes include assessment of the following: procedural time and clinical utility measures at the intra-operative and post-procedure time points (see Appendix C, Definitions); major adverse events (see Appendix C, Definitions), injury healing (as determined by maximum transverse diameter at the site of injury), secondary interventions, endoleak, device migration, device patency, device integrity, and device collapse through the 5-year time point.

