5.2 Endpoints

The primary safety endpoint will be all-cause and aortic-injury-related mortality at 30 days.

The primary effectiveness endpoint will be device success, defined as technical success (i.e., successful access of the injury site and deployment of the Zenith® TX2® Low Profile Endovascular Graft in the intended location, and endovascular graft patency upon completion of deployment) with none of the following at 30 days:

- Device collapse;
- Type I or type III endoleak requiring reintervention; or
- Conversion to open surgical repair.

The secondary endpoints include an assessment of the following:

- At the intra-operative and post-procedure time points:
 - Procedural time and clinical utility measures (see Appendix C, Definitions);
- Through the 5-year time point:
 - Major adverse events (see Appendix C, Definitions),
 - Injury healing (as determined by maximum transverse diameter at the site of injury),
 - Secondary interventions,
 - Endoleak,
 - Device migration,
 - Device patency,
 - Device integrity, and
 - Device collapse.

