5.6 Point of Enrollment

Point of enrollment will be based on the intent-to-treat population, and is defined to include any patient in whom the treatment procedure is initiated. More specifically, once a procedure has begun (i.e., cutdown or percutaneous access initiated), the patient will be included in the intent-to-treat population. The patient's informed consent will be obtained and assessment of the patient's conformance to the inclusion/exclusion criteria will occur prior to the procedure.

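### Section 7.4 handles missing endpoint data without using follow-up time, and nothing else in the plan says how rates through 5 years are to be estimated

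*Combined protocol and SAP*

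**What the plan says.** Section 5.2 lists major adverse events (MAE), injury healing, secondary interventions, endoleak, migration, patency, integrity and collapse under the heading "Through the 5-year time point". Section 3.2 likewise follows these outcomes, ending with "device collapse through the 5-year time point". Sections 3.3 and 7.2 say that all endpoints are analyzed descriptively, without inference.

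The intent-to-treat population in section 5.6 takes in "any patient in whom the treatment procedure is initiated". Under section 6.10 a patient's follow-up stops at death, withdrawal or loss, 30 days after failed deployment, or at "Conversion to open surgical repair + 30 days".

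Section 7.4 gives three strategies:
- Best-available data, for missing imaging: investigator readings, clinical sequelae or later scans.
- Case deletion: if enough analyzable patients remain for the power of the primary endpoints, "then case deletion will be the method of choice for that analysis".
- Multiple imputation, for missing endpoint data generally. The only model described is for the primary endpoints: Bernoulli draws at the observed proportion, with no covariates anticipated.

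A tipping-point analysis is optional. No section mentions Kaplan-Meier, cumulative incidence, censoring, competing events or per-visit denominators.

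**The concern.** A cumulative rate through 5 years needs a rule for patients whose follow-up stops early without an event. Case deletion treats the two kinds of early leaver differently. A patient who has an event in year 1 and is lost in year 2 has a known answer and stays in the numerator and denominator. A patient lost event-free in year 2 has an unknown 5-year answer and is removed, together with two years of event-free observation. Covariate-free imputation fills the gap at the same inflated proportion. For device outcomes, death and conversion also prevent later events, and the plan does not say how they count.

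These rates are the long-term safety and durability evidence. Section 7.5 expects the data to serve as prior information for later device variations, so an avoidable bias could be carried forward. If the denominator is left open, one dataset can also be reported as noticeably different rates.

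**Working it through.** **The plan's own figure.** Section 7.1 uses n = z²p(1−p)/Δ² with p = 0.076 and Δ = 0.08. That is 1.96² × 0.076 × 0.924 / 0.0064 = 42.15, rounded up to 43, as stated. The section adds: "A total of 50 patients will be enrolled to account for possible loss to follow-up or withdrawal from the study". The allowance is therefore 7 of 50 (14%).

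**When case deletion applies.** Section 7.4 gives no number for its condition. I take 43, the only candidate in the documents, so at most 7 of 50 may be missing. The binomial chance of 7 or fewer missing is 0.88 at 10% missing, 0.52 at 15%, 0.19 at 20% and 0.007 at 30%.

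**Assumptions (the documents give no 5-year rates).** Event, death and loss times are independent with constant hazards. Loss risk alone is 15% over 5 years, varied below. Lost patients are deleted. Deaths without a device event are kept as event-free.

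**Device-type endpoint.** Event risk is 20% and death risk 12% over 5 years. The cumulative hazards are:
- event a = −ln 0.80 = 0.2231
- death b = −ln 0.88 = 0.1278
- loss c = −ln 0.85 = 0.1625

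True cumulative incidence = a/(a+b) × (1 − e^−(a+b)) = 0.2231/0.3510 × 0.2960 = 18.8%.

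With loss, h = a+b+c = 0.5135 and 1 − e^−h = 0.4016.
- Observed events: 0.2231/0.5135 × 0.4016 = 17.5%
- Lost event-free: 0.1625/0.5135 × 0.4016 = 12.7%, about 6 of 50
- Case deletion: 0.1745/(1 − 0.1271) = 20.0%
- Events over all enrolled: 17.5%

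**MAE composite.** Death and conversion are components (Appendix C), so only loss or other early end of follow-up creates missing data. I assume 15% with an MAE by 30 days and a 10% risk later, with loss acting on the late phase. The true rate is 1 − 0.85 × 0.90 = 23.5%.

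The late hazards are 0.1054 (event) and 0.1625 (loss), summing to 0.2679, and 1 − e^−0.2679 = 0.2350.
- Observed events: 0.15 + 0.85 × 0.1054/0.2679 × 0.2350 = 22.9%
- Lost event-free: 0.85 × 0.1625/0.2679 × 0.2350 = 12.1%
- Case deletion: 0.2286/(1 − 0.1212) = 26.0%
- Events over all enrolled: 22.9%

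**Range over loss.** The last two columns are the proportion among patients with a known answer. That is what case deletion reports, and what covariate-free imputation reproduces on average.

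| Loss risk | Missing, device / MAE | Device (true 18.8%) | MAE (true 23.5%) |
|---|---|---|---|
| 10% | 8% / 8% | 19.6% | 25.1% |
| 15% | 13% / 12% | 20.0% | 26.0% |
| 20% | 17% / 16% | 20.4% | 27.0% |
| 40% | 34% / 32% | 22.7% | 32.1% |

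At 15% loss the chance that 7 or fewer are missing is about 0.70 (device) and 0.74 (MAE), so case deletion would usually apply. At 40% it is about 0.001 and 0.003. The last row therefore shows what imputation would give if the 30-day model were extended, and is not a case-deletion result. Events over all enrolled would there be 15.0% and 21.7%.

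**The case against.** The strongest reply is that section 7.4 does more than delete and impute, and that the late endpoints are secondary and descriptive. Much of this stands.

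- A reader might infer that deletion and imputation are the only methods offered. They are not: best-available data covers missing imaging, on which most late device endpoints rest, and a tipping-point analysis is possible. Neither supplies 5-year status for a patient who never returns, or treats death as a competing event.
- A reader might infer that Bernoulli imputation is prescribed at 5 years. The text states it for the primary endpoints, which are at 30 days. The 5-year gap is an unspecified model.
- A reader might infer that stopping follow-up after conversion biases MAE. It does not: conversion is itself an MAE, so the patient is already counted.
- Per-visit proportions among patients imaged are a sound descriptive summary if labelled so. They are not cumulative rates.
- The bias is small beside sampling error. One patient in 50 is 2 points, and the 95% half-width for 18.8% of 50 is 1.96 × √(0.188 × 0.812/50) = 10.8 points. That limits the importance of the point, but it does not justify choosing an estimator that is biased in a known direction.

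Section 10.5 asks that patients discontinued for safety or lack of effectiveness still be followed if possible. It does not say whether this overrides the 30-day end of follow-up after failed deployment in section 6.10.

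**Conclusion.** The point holds as a gap in method with a modest bias. The written rules do not use follow-up time, their condition is tied to the primary endpoints, and no other section supplies an estimator or denominator for the 5-year endpoints. Where case deletion would still apply (about 12-13% missing, taking 43 of 50 as the required number), it overstates a cumulative rate by about 1 point for a device endpoint and about 2.5 points for MAE. These sizes rest on assumed rates and independent loss.

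A reader might go further and quote biases of 4 points or more as the result of case deletion. The documents do not support that. Such figures need about a third of patients missing, where the plan's own condition would almost certainly have switched deletion off, or they need event-free deaths to be deleted, which no section calls for. Nor is the direction fixed for every reading: events over all enrolled is biased downward.

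One inconsistency remains for failed deployment without conversion. These patients are in the intent-to-treat population, and all-cause death is an MAE component through 5 years, yet section 6.10 ends their follow-up at 30 days.

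**What to change.** In section 7.4, limit the case-deletion and Bernoulli rules to the 30-day primary endpoints. For endpoints through 5 years, state that all enrolled patients contribute until last assessment, and report:
- Kaplan-Meier estimates for all-cause death and for the MAE composite.
- Cumulative incidence (Aalen-Johansen) for secondary interventions and device outcomes, with death, and conversion where relevant, as competing events.
- Per-visit proportions for imaging findings, with the number assessed as the stated denominator.

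All are descriptive and fit section 7.2. They too assume that loss is unrelated to outcome, so numbers at risk should be shown.

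For failed deployments, reconcile section 6.10 with the 5-year MAE definition, or state that these patients are censored when follow-up ends.

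The cost is a few sentences in the plan and a little more analysis work with standard software. Sample size and visit schedule do not change.

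### Section 7.4 imputes missing primary outcomes at the fixed observed proportion, which omits the uncertainty in that proportion and, when no failure is seen, makes every missing patient a certain success

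*Combined protocol and SAP*

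**What the plan says.** Section 7.4 (Missing Data) lists three strategies.

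- **Best available data.** This may be used for missing imaging. Investigator measurements, clinical sequelae or later scans can stand in for a missing core laboratory reading.
- **Case deletion.** If enough analyzable patients remain for sufficient power on the primary endpoints, "then case deletion will be the method of choice for that analysis".
- **Multiple imputation.** For missing primary endpoint data the method will "generate random Bernoulli observations with probabilities equivalent to the proportion of (non-missing" entries. On covariates: "It is anticipated that no covariates will be used for this model". On the mechanism: "Unless evidence suggests otherwise, missing at random data will be assumed". The results may provide "estimates of the missing data that can be utilized in estimating event rates and confidence bounds". On software: "The computations will be performed using PROC MI and PROC MIANALYZE in SAS version 9.1 or later". A multiple-imputation textbook is also cited.

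The section ends: "Additional analyses of missing data may be performed as appropriate, including a tipping point analysis".

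Section 7.3 (Site-level Poolability) anticipates that "the primary and secondary endpoint measures may be related to covariates that reflect this severity, which are in turn related to outcome". Sections 3.3 and 7.2 make all endpoints descriptive. Section 7.1 sizes the study by the precision of a 95% confidence interval.

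**The concern.** Rubin's combining rules, which PROC MIANALYZE applies, give a valid variance only if each imputed data set also reflects uncertainty about the parameter behind the draws. Drawing every missing outcome at the observed proportion leaves that component out. The section therefore names standard procedures and describes a rule that does not meet their requirement, and two programmers could implement it differently.

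The rule breaks down when the observed failure proportion is zero. Every draw is then the same, and patients whose outcome is unknown enter the denominator as successes.

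With no covariates, missing at random also has nothing to condition on. For a patient without the endpoint, the assumption becomes missing completely at random, which is stronger than the one the section names.

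What is at stake is the stated precision of the primary endpoints. Precision is the study's sizing basis, and section 7.5 expects the data to serve as prior information for later device variations.

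**Working it through.** **Inputs from the documents.** Planned 30-day mortality 7.6%, margin 8 points, 43 patients required, 50 enrolled (section 7.1).

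**Assumptions.** The case-deletion threshold is taken as 43, because the plan refers to power but contains no power calculation. Imputation then starts at 50 − 42 = 8 missing. Device failure rates of 1% to 5% are assumed, because none is given. Section 7.4 does not state the number of imputations, so the standard error results below are for many imputations unless noted.

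**1. The plan's own figure.** n = 1.96² × 0.076 × 0.924 / 0.08² = 42.15, rounded up to 43. It reproduces. Appendix E sums to 112/1477 = 7.58%, which agrees with 7.6%.

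**2. No failure observed.** The draw probability for failure is 0, so all m missing patients are imputed as successes in every data set and the between-imputation variance B is 0. The exact (Clopper-Pearson) 95% lower limit for n/n is 0.025^(1/n).

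| Observed | Lower limit, observed data | After imputation to 50/50 |
|---|---|---|
| 42/42 | 91.6% | 92.9% |
| 30/30 | 88.4% | 92.9% |

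The limit rises by 1.3 and 4.5 points without any new information. If the probability is drawn from Beta(0.5, 42.5) instead, the chance that at least one of the 8 missing patients is imputed as a failure is 8.3%, not 0.

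**3. How likely that case is.** P(no failure in 42) = (1 − rate)^42.

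| Rate | P(no failure in 42) |
|---|---|
| 7.6% (planned mortality) | 3.6% |
| 5% (assumed device failure) | 12% |
| 2% (assumed) | 43% |
| 1% (assumed) | 66% |

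**4. Events observed.** Write N = 50, n = N − m observed, q = 1 − p.

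- Within-imputation variance: W = pq/N.
- Fixed-proportion draws: B = pq·m/N².
- Proper draws: B = pq·[m/N² + (m/N)²/n]. W + B then equals pq/n, the correct value.

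The ratio of the standard error under fixed draws to the correct one is √[n(1/N + m/N²)] = √[1 − (m/N)²].

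| Missing | Ratio | Understatement |
|---|---|---|
| 8 | √0.9744 = 0.987 | 1.3% |
| 12 | √0.9424 = 0.971 | 3% |
| 20 | √0.8400 = 0.917 | 8% |

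With 20 imputations the ratios at 8 and 20 missing are 0.991 and 0.923. With 5 imputations they are 1.00 and 0.942. The extra term for a finite number of imputations hides part of the shortfall but does not correct it.

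**The case against.** The case on the other side has several parts.

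- **Imputation is the last resort.** Case deletion comes first, and substitute readings may already have filled imaging gaps. At least 8 of 50 patients must lack a 30-day outcome under the 43-patient assumption. This stands and limits the reach.
- **The effect is small at the threshold.** This also stands. In a simulation at 7.6% with 42 observed and 20 imputations, the combined variance was about 0.955 of the true variance. A plain complete-case variance already gives 0.976, so about half of that gap is ordinary small-sample bias and not due to imputation.
- **The exact interval on 50/50 is not the plan's named method.** True: the plan names PROC MIANALYZE. With 50/50, though, W and B are both 0, so Rubin's rules give an interval of zero width. A normal-approximation interval on 42/42 would also have zero width, which is why exact limits are used here to show the gain in apparent sample size.
- **The fixed-proportion wording may be shorthand for proper imputation.** Possibly, since the textbook and the SAS procedures point that way. Then the text still needs correcting, because it specifies something else.
- **All endpoints are descriptive.** No success rule can flip, which keeps the severity down. Section 7.4 nevertheless applies imputation to confidence bounds.

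A stronger reading is tempting: because section 7.3 expects outcome to follow severity and the imputation has no covariates, a reader might infer that imputation biases the mortality rate downward. The documents do not support that. They do not say that more severely injured patients are more likely to be missing, and they give no severity-specific rates. Covariate-free imputation targets the complete-case rate, so any such bias would be the same under case deletion, the first-line method. The absence of covariates is also only anticipated. Nor do the documents show that imputing within severity strata would be better: with 42 × 0.076 ≈ 3 deaths expected, stratum rates would be very noisy.

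**Conclusion.** The imputation rule in section 7.4 is wrong as written and modest in size. It omits parameter uncertainty, conflicts with the procedures named beside it, and degenerates when no failure is observed.

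The zero-failure case is unlikely for all-cause mortality at the planned rate. It is plausible for device success if failures are rare, but the documents give no rate to settle that. With only 8 missing, the loss in standard error when events occur is slight; it matters only with much heavier missingness.

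The label missing at random should read missing completely at random for the covariate-free model, and the same assumption underlies case deletion. The tipping point analysis would address departures from it, but it is optional.

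These conclusions rest on 43 being the case-deletion threshold and on substitute data not having closed the gaps. A claim that the reported rates will be biased by severity goes beyond the documents.

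**What to change.** In section 7.4:

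1. Replace the fixed-proportion rule. For each imputation, draw p from Beta(x + 0.5, n − x + 0.5), where x is the number of events among n observed patients, then draw the missing outcomes from Bernoulli(p). Reconcile the wording with PROC MI and PROC MIANALYZE, so that one algorithm is specified.
2. State that both covariate-free imputation and case deletion assume missing completely at random.
3. Make the tipping point analysis mandatory whenever any primary endpoint data are missing. As there is no success threshold, it should show the rate and interval over the whole range from none to all of the missing patients failing. With 0/42 observed and 8 missing, that range runs from 0% to 8/50 = 16% (exact 95% interval 7.2% to 29.1%).

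**Cost.** SAP wording and a few lines of code. The Beta draw moves rare event rates up slightly. At a true 2% with 42 observed, the mean imputed probability is (0.84 + 0.5)/43 = 3.1%, and 8/50 × 1.1 points ≈ 0.2 point. The variance becomes slightly conservative: simulated ratios to the true variance were about 1.02, 1.04 and 1.07 with 42, 38 and 30 observed.
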